8.1.1 Screening and Baseline Measurements

In a window of time defined by less than 12 hours prior to initiation of first PE on study (as detailed in section 4.2) and study drug, all subjects will undergo a thorough examination to investigate their suitability for participation in the study. Inclusion and exclusion criteria will be checked. A screening log should be maintained, recording the reason when subjects are screened but not included in the study. If the subject satisfies the inclusion and exclusion criteria, informed consent will be obtained prior to randomisation and additional assessments will be performed within 15 minutes to 6 hours prior to initiation of the first PE on study and study drug. If done within 6 hours of starting study drug, the chemistry, haematology and coagulation assessments can be considered baseline and do not need to be repeated (see Table 10).

The following screening procedures must be performed prior to randomisation (see Table 10):

- Check in/exclusion criteria
- Demographic data (e.g. age, height, weight, body mass index (BMI), ethnic origin and number of years of formal education completed). The balance should have a precision of at least 0.5 kg. Body weight will be recorded in kg with 1 decimal. The BMI will be calculated from the weight and height: $BMI (kg/m^2) = weight (kg) / height (m) \times height (m)$.
- Medical history
- Prior and concomitant medication taken during the 30 days prior to the screening examination are to be documented. Concomitant medication from the 30 days prior to screening until follow-up or started during the course of the study will be recorded on the Concomitant Medications page of the CRF. Concomitant medications initiated, stopped, up-titrated or down-titrated for an AE will also be recorded on a specific Concomitant Medications page of the CRF.
- Clinical assessment will include physical examination and vital signs (blood pressure and heart rate at rest, body temperature),
- Obtain signed and dated informed consent
- The Glasgow Coma Score will be determined using the Glasgow Coma Scale (original scale), which is a neurological scale that measures the conscious state of the subject. The best eye, verbal and motor responses will be scored according to the scale and the separate scores added up to obtain the final score, ranging from 3 to 15.
- Assessment of clinically relevant bleeding

- Urinalysis (local laboratory)

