8.3.7 Adverse Events

It is the responsibility of the Investigator to document all AEs which occur during the entire study period, up to the last follow-up visit.

All AEs occurring after the start of the study must be reported. Subjects entry into the study is defined as the time at which informed consent is obtained. All subsequent AEs, irrespective of whether no drug, active drug or placebo has been administered, must be recorded regardless of whether or not they are considered to be drug related.

At each assessment, all AEs either observed by the Investigator or one of his clinical collaborators, or reported by the subject spontaneously or in a response to a direct question must be evaluated by the Investigator and noted in the AE sections of the subject's CRF.

Any clinically significant changes in laboratory parameters and all deviations of coagulation parameters outside normal range will be recorded as (an) AE(s) in the relevant section of the CRF.

The non-leading question "Have you felt different in any way over the last few days?" will be asked at baseline and the question "Do you feel different in any way since starting the new treatment/the last assessment?" will be asked at regular intervals throughout the study. The responses will be recorded in the subject's CRF.

The nature of each event, date and time of onset, duration, severity and relationship to treatment should be established. Details of changes to the dosage schedule or any corrective treatment should be recorded on the appropriate pages of the CRF.

The Investigator should follow-up subjects with AEs until the event has subsided (disappeared) or until the condition has stabilised. Reports relative to the subject's subsequent course must be submitted to the clinical study monitor.

For more details, refer to section 9.

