9.1.6 Reporting of Adverse Events

All AEs occurring after the start of the study must be recorded until end of follow-up (1y), or until subject withdrawal. Subjects entry into the study is defined as the time at which informed consent is obtained. All subsequent AEs, irrespective of whether no drug, study drug or placebo was administered, must be recorded on specific AE pages of the respective CRF, regardless of whether or not they are considered to be study drug related. AEs occurring from study drug initiation until 30 days post study drug discontinuation (inclusive) are defined as treatment emergent.

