10.3 Evaluation of Safety and Tolerability Parameters

All safety parameters (physical examination, vital signs, bleeding, ECG-parameter, biochemistry/haematology and ADA evaluations, concomitant medications (including PE characteristics) and AEs) will be summarised descriptively by treatment. Quantitative variables will be described by n, mean, standard deviation, median, minimum and maximum. Qualitative variables will be described by frequency tables containing counts and percentages. Additionally, shift tables will be provided for the safety laboratory parameters (within, below or above normal range) from pre-study to post-dose.

The AEs will be coded according to MedDRA and tabulated by system organ class, preferred term and lower level term. An AE will be referred to by the treatment and time point after which it occurred, i.e. any AE occurring before the dosing will be counted as a baseline AE and will be considered as a treatment-emergent AE only if the severity or relation to drug changes.

No formal statistical testing will be performed on the safety data.

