### 6.4.1 Adverse Events

All AEs will be classified using the Medical Dictionary for Regulatory Activities (MedDRA) coding dictionary version 15.0 or higher.

Events will be classified as *treatment-emergent* if they started on or after date of first dose of study drug. Treatment-emergent adverse events are therefore a subset of all adverse events. If an event start date is partial, then the start month, year or stop date will be used to determine if the event is treatment-emergent. If the classification of the AE cannot be determined from the data available, then the event will be considered treatment-emergent.

The following presentations will be produced by treatment group and overall:

*Treatment-emergent events:*

- A general summary table reporting the number of events and the number and percentage of subjects with events will be presented by treatment group. The following categories will be included in this general summary table:
  - The number of subjects having any adverse event.
  - The number of subjects having at least one treatment-emergent adverse event.
  - The number of subjects having at least one TTP-related treatment-emergent adverse event.
  - The number of subjects having at least one PE-related treatment-emergent adverse event.

- 
- The number of subjects having at least one drug-related treatment-emergent adverse event (defined as related or possibly related to study treatment).
  - The number of subjects having at least one treatment-emergent adverse event leading to discontinuation of study drug (defined as having study treatment action taken recorded as “study drug discontinued”).
  - The number of subjects having at least one treatment-emergent adverse event leading to interruption of study drug (defined as having study treatment action taken recorded as “study drug interrupted”).
  - The number of subjects having at least one treatment-emergent adverse event leading to interruption or discontinuation of study drug (defined as having study treatment action taken recorded as either “study drug interrupted” or “study drug discontinued”).
  - The number of subjects having treatment-emergent adverse events with death as outcome.
  - The number of subjects having at least one serious adverse event.
  - The number of subjects having at least one serious treatment-emergent adverse event.
  - The number of subjects having at least one serious treatment-emergent drug-related adverse event.
- 

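### SAP 6.4.1 opens the treatment-emergent window by calendar date, so AEs known to have begun before the first dose on the dosing day are counted as treatment-emergent, contrary to protocol 10.3 and 9.1.6

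*SAP*

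**What the plan says.** **SAP 6.4.1** makes an AE treatment-emergent "if they started on or after date of first dose of study drug". For a partial start date, "then the start month, year or stop date will be used to determine if the event is treatment-emergent". The residual rule is inclusive: "If the classification of the AE cannot be determined from the data available, then the event will be considered treatment-emergent". Onset time appears in none of these rules, and nothing is said about an event that starts on the dosing date before the dose.

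**Protocol 10.3** says that "any AE occurring before the dosing will be counted as a baseline AE", and that it becomes treatment-emergent only if its severity or relation to drug changes. **Protocol 9.1.6** fixes the window: "AEs occurring from study drug initiation until 30 days post study drug discontinuation (inclusive) are defined as treatment emergent".

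**AE collection** begins before dosing. Protocol 9.1.6 says: "Subjects entry into the study is defined as the time at which informed consent is obtained"; all AEs after that point are recorded. Protocol 8.1.1 lists AE recording among the baseline procedures, and protocol 9.2.2.1 puts SAEs that arise between consent and first drug on the AE pages of the CRF.

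**Times.** Protocol 8.3.7 asks for clock time of onset: "The nature of each event, date and time of onset, duration, severity and relationship to treatment should be established". SAP section 3 takes the first dose to the minute for the primary endpoint.

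**SAP 6.1.5**, which lists changes from the protocol, does not mention this one.

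**The concern.** In most trials a date rule for the start of the window costs little, because screening is days before dosing. Here the sequence is compressed. Consent, screening, baseline assessments and the first bolus normally fall within half a day, in patients who are acutely ill. The dosing date is therefore where pre-dose AEs collect, and on that date the SAP's rule and the protocol's rule give opposite answers.

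A complication of TTP or of a procedure that began after consent but before the bolus cannot have been caused by study drug. Under SAP 6.4.1 it still enters the treatment-emergent overview and the tables by system organ class, severity and relationship, and, where it applies, the serious, TTP-related and PE-related counts. Events unrelated to allocation raise both arms' counts and pull a ratio of the two towards 1.

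**Working it through.** The documents give no figure on this point, so there is none to reproduce. Two things can be checked: whether the rules conflict, and how often the conflict would apply to a pre-dose AE.

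**1. The rules side by side.** Take an AE that starts after consent at 09:00, with the first dose at 11:00 the same day.
- SAP 6.4.1: start date equals dosing date, so treatment-emergent.
- Protocol 10.3: before dosing, so a baseline AE unless severity or relation changes.
- Protocol 9.1.6: before drug initiation, so outside the window.

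The SAP's default for undetermined cases does not explain this result. Nothing is undetermined here: onset time is known and the rule ignores it.

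**2. Length of the pre-dose window, W.** Protocol 8.1.1 sets screening "In a window of time defined by less than 12 hours prior to initiation of first PE on study". The first dose comes 15 min to 6 h before that PE (protocol 7.2). So:
- dose 15 min before PE: W is at most 12 − 0.25 = 11.75 h;
- dose 6 h before PE: W is at most 12 − 6 = 6 h.

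**3. Share of pre-dose AEs on the dosing date.** Assumptions, not in the documents: onset is uniform between consent and dose, and dosing hour T (hours after midnight) is uniform over 24 h.
- For given T and W, the share is min(T, W)/W.
- Averaged over T: (1/24) × [W/2 + (24 − W)] = 1 − W/48.

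| W (h) | 1 − W/48 | Share counted as treatment-emergent |
|---|---|---|
| 12 | 1 − 0.250 | 75.0% |
| 11.75 | 1 − 0.245 | 75.5% |
| 6 | 1 − 0.125 | 87.5% |
| 2 | 1 − 0.042 | 95.8% |

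**4. Sensitivity to dosing hour.** If first doses fall evenly between 08:00 and 20:00, the mean share at W = 11.75 h is 95% and the lowest is 8/11.75 = 68%; for W up to 8 h it is 100%. The share falls below half only when T is less than W/2, that is, for doses before about 05:52 at W = 11.75 h or before 03:00 at W = 6 h. A dose at 03:00 with W = 11.75 h gives 3/11.75 = 26%.

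**5. What this does not give.** The denominator is AEs recorded between consent and first dose. The documents do not allow an estimate of how many there will be, so the share of treatment-emergent AEs that is misclassified cannot be computed. Each subject contributes at most about 12 pre-dose hours, against PE treatment plus 30 days of study drug (up to 90 days in all) and then follow-up.

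**6. Direction of effect.** Purely as illustration, with 55 subjects per arm (110 randomised 1:1), suppose 5 versus 2 subjects have a given event after dosing and 3 others in each arm have it only before dosing. The ratio moves from 5/2 = 2.5 to 8/5 = 1.6; the difference stays at 3 of 55. These counts are assumed and say nothing about likely size.

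**The case against.** The case against giving this weight is substantial, and much of it stands.

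- **Many pre-dose events never reach the AE data.** Events before consent are not AEs in this trial, which may cover reactions to a PE given before randomisation. Protocol 8.3.3, the bleeding section, sends clinically relevant findings seen before drug initiation to Medical History. Active bleeding is an exclusion criterion. Pre-existing conditions that do not worsen are not AEs (protocol 9.1.1). Where local rules allow the study to start before consent (protocol 11.3), there may be no pre-dose window. This stands and limits the number of events. It does not empty the category, because protocol 9.1.6 requires all AEs after consent to be recorded.
- **The bleeding comparison is protected.** A reader might infer that the date rule distorts the main safety question. The documents do not support that. SAP 6.4.6 tabulates clinically relevant bleeding and the modified ITP score by treatment and visit, without the treatment-emergent flag, and both are also assessed at baseline.
- **The rule is the same in both arms, no formal safety testing is planned, and all AEs are listed.** This stands. Equal counts are not guaranteed, since the investigator learns the allocation at randomisation (protocol 7.5) and baseline AE recording follows randomisation, but nothing in the documents shows an imbalance. Drug-related tables should be little affected, because relatedness depends on timing relative to administration.
- **Counting same-day events as treatment-emergent is a cautious safety convention.** That is a fair reason for the default when time is unknown. It is not a reason to override a known onset time against the protocol's definition.
- **Onset time may not be in the database.** The CRF is not among the documents, and the SAP's other AE derivations refer only to dates. This stands, and the fix allows for it.

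**Conclusion.** The conflict is real and undeclared: SAP 6.4.1 counts as treatment-emergent a class of AEs that protocol 10.3 calls baseline and protocol 9.1.6 places outside the window. Because the pre-dose window is normally under 12 h, most AEs in that class would be affected: about 75% at 12 h and 88% at 6 h, given uniform onset and dosing hour, with lower shares only for subjects dosed in the early hours after midnight.

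It would be wrong to read those percentages as the share of safety events that is misclassified. They apply to pre-dose AEs alone, whose number is unknown and probably small relative to all treatment-emergent AEs. The primary efficacy analysis and the SAP 6.4.6 bleeding tabulations are not affected. What remains is avoidable contamination of the general, serious, TTP-related and PE-related treatment-emergent tables in both arms, and a departure from the protocol that the SAP should either remove or state.

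**What to change.** In SAP 6.4.1:

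1. Class an AE as treatment-emergent if its onset date and time is at or after the date and time of first study drug.
2. If onset time is missing on the dosing date, keep the present default and count the AE as treatment-emergent.
3. Count an AE with a known pre-dose onset on the dosing date as a baseline AE, treatment-emergent only if its severity or relation to drug changes, as in protocol 10.3. Worsening during drug administration already opens a new AE record under protocol 9.1.3, so it carries its own post-dose onset.

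First confirm that AE onset time is in the analysis database. If it is not, keep the date rule and list the departure from protocol 10.3 in SAP 6.1.5.

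The cost is two or three sentences in the SAP and one change to the AE flag. First-dose time is already derived for the primary endpoint, and onset time needs no new collection if it was captured as protocol 8.3.7 requires.

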Inhibition of the biomarker RICO was observed in all doses groups ranging from 70% inhibition in the 2 mg dosing group to approximately 90% inhibition in the other SD groups. Reversal towards basal levels took place after approximately 72 h post dosing. A rapid and sustained inhibition of approximately 90% was observed after dosing in both MD groups. Values returned to basal levels at day 15 and day 22 after 7 days and 14 days MD respectively. In all dose groups of the SD part of the study complete RICO inhibition (defined as values < 20%) was observed from 4-18 h (2 mg), 12-18 h (4 mg), 4-24 h (8 mg), 4-36 h (10 mg) and 4-48 h (16mg) after dosing. In both groups of the MD part of the study RICO was completely inhibited from 2-168 h after dosing, i.e. from day 1-8 (7 day) and from 2-360 h after dosing, i.e. day 1-16 (14 day). A summary of the main PD findings is provided in Table 6.

Table 6: Summary of main PD results (number (%) of subjects with event).

Dose level	Subjects (n)	RICO < 20%		vWF < 50%	FVIII < 50%	
		Subjects (%)	Start (h)*			Stop (h)*
SD						
2 mg	3	2 (67)	2-4	12-18	3 (100)	0 (0)
4 mg	3	2 (67)	4-6	18-36	1 (33)	1 (33)
8 mg	3	3 (100)	2-4	18-48	3 (100)	3 (100)
16 mg	3	3 (100)	1-4	48	0 (0)	2 (67)
10 mg	3	3 (100)	2-6	24-36	3 (100)	3 (100)
Placebo	5	0 (0)	NA	NA	0 (0)	0 (0)
MD						
10 mg (7d)	6	6 (100)	2-4	168-192	5 (83)	3 (50)
Placebo (7d)	2	0 (0)	NA	NA	0 (0)	0 (0)
10 mg (14d)	6	6 (100)	2-4	336-360	5 (83)	5 (83)
Placebo (14d)	2	0 (0)	NA	NA	0 (0)	0 (0)

* Time relative to first administration

NA: not applicable

Safety

Overall the study drug ALX-0081 was well tolerated and there was no difference in the number of subjects with AEs and their respective severity between the ALX-0081 treatment groups and placebo. In all doses of the SD part of the study the related AEs were low and in all verum categories no more than 1 subject reported 1 related AE. In the MD 7 days part of the study, a total of 5/6 subjects (83%) reported 13 related AEs in the verum group compared to 2/2 subjects (100%) reporting 2 related AEs in the placebo group. In the MD 14 days part of the study a total of 6/6 subjects (100%) reported 46 related AEs in the verum group compared to 1/2 subjects (50%) reporting 1 related AE in the placebo group. A dose

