- Treatment-emergent AEs and SAEs will be summarised by system organ class and preferred term. The number of events and the number and percentage of subjects having each event will be presented.
  - Treatment-emergent AEs and SAEs will be summarised by system organ class, preferred term and severity. The number of events and the number and percentage of subjects having each event will be presented for the maximum severity reported for each event. The maximum severity per preferred term will be evaluated for each subject and the resulting dataset will be used to present the summary. Any missing severity will be left as missing and categorised as such.

- 
- Treatment-emergent AEs and SAEs will be summarised by system organ class, preferred term and relationship to study drug. The number of events and the number and percentage of subjects having each event will be presented for the most conservative relationship to study drug reported for each event. For example, if a subject has both a related and a possibly related event in the same preferred term, the related event will be taken for summary. The most conservative relationship per preferred term will be evaluated for each subject and the resulting dataset will be used to present the summary. Any missing relationship will be left as missing and categorised as such.
  - Treatment-emergent AEs that lead to discontinuation of study drug will be summarised by system organ class and preferred term. The number of events and the number and percentage of subjects having each event will be presented.
  - Treatment-emergent AEs that lead to interruption of study drug will be summarised by system organ class and preferred term. The number of events and the number and percentage of subjects having each event will be presented.
  - Treatment-emergent AEs that lead to interruption or discontinuation of study drug will be summarised by system organ class and preferred term. The number of events and the number and percentage of subjects having each event will be presented.

Note: If a subject records multiple AEs with the same preferred term, these shall be summarised once within the count for n (%) of subjects, yet each event will be counted within the number of reports n\* of each AE. AEs that have grade changes reported in the CRF shall be counted once, at the maximum severity reported.

*All adverse events:*

All recorded adverse events will be listed.

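### SAP 6.4.1 promises event counts in the AE tables by severity and by relationship, but builds both from one record per subject and preferred term, contradicting its own Note that every event is counted

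*SAP*

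**What the plan says.** The list of AE tables in SAP 6.4.1 begins with a SOC and preferred-term table that gives events and subjects with no reduction step. Two further tables cross the same rows with severity and with relationship to study drug.

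- **Severity table, content:** "The number of events and the number and percentage of subjects having each event will be presented for the maximum severity reported for each event".
- **Severity table, source data:** "The maximum severity per preferred term will be evaluated for each subject and the resulting dataset will be used to present the summary".
- **Relationship table, source data:** "The most conservative relationship per preferred term will be evaluated for each subject and the resulting dataset will be used to present the summary". The SAP illustrates this with a subject who has a related and a possibly related event under one term: only the related one goes into the summary.
- **Note closing the list:** several AEs of one subject under one term add a single subject to the subject column, but for the event column the Note says "yet each event will be counted within the number of reports". The Note exempts no table. It adds: "AEs that have grade changes reported in the CRF shall be counted once, at the maximum severity reported".

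The section sets the maximum per preferred term only. It has no rule for a subject with several terms of different severity or relationship within one SOC. Separately, Protocol 9.1.3 has the investigator close an AE that worsens on study drug and open a new one at the higher intensity, so a single episode can produce two records.

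**The concern.** A dataset cut to one record per subject and term can supply subject counts. It cannot supply a count of events, because the repeats have already been removed. The SAP nevertheless uses it for both columns and then says in the Note that each event is counted. A programmer has to choose between a general Note and two table-specific sentences, and the specific sentences point towards the collapsed count.

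Incidence, severity and relationship of treatment-emergent AEs form a listed secondary endpoint (Protocol 4.1.2). These two are the only planned tables that show events by preferred term and severity, or by preferred term and relationship. The bleeding summaries in SAP 6.4.6 count subjects and scores by visit and do not replace them.

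Event counts matter most when nearly every subject has at least one event. Protocol 2.4.2 gives an example from the 14-day Phase I group: "a total of 6/6 subjects (100%) reported 46 related AEs in the verum group". The subject percentage there is already at its ceiling, so only the event count shows the repetition. The same section reports more related AEs with longer treatment, including more bruises and bleedings, and this trial allows up to 90 days of treatment.

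**Working it through.** There is no planned figure to reproduce. The check applies the two rules to one small dataset and then bounds the effect in the Phase I group.

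**Hypothetical data (an assumption, not trial data).** Seven AEs, three subjects, two terms in one SOC:

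- Subject 1: epistaxis mild/related, mild/related and moderate/possibly related; haemoptysis mild/possibly related.
- Subject 2: epistaxis mild/related and mild/possibly related.
- Subject 3: haemoptysis severe/not related.

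**Step 1, all records.** Epistaxis: 3 + 2 = 5 events in 2 subjects. Haemoptysis: 1 + 1 = 2 events in 2 subjects. SOC: 7 events in 3 subjects.

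**Step 2, reduced dataset, read literally.** One record per subject and term leaves four: subject 1 epistaxis (moderate, related), subject 1 haemoptysis (mild, possibly related), subject 2 epistaxis (mild, related), subject 3 haemoptysis (severe, not related).

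| Row | Events, all records | Events, reduced | Subjects |
|---|---|---|---|
| Epistaxis | 5 | 2 | 2 |
| Haemoptysis | 2 | 2 | 2 |
| SOC | 7 | 4 | 3 |

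In preferred-term rows, events equal subjects. In the SOC row, the 4 is the number of subject-by-term pairs: neither the 7 events nor the 3 subjects. The plain SOC and preferred-term table would show 5, 2 and 7, so the tables do not reconcile.

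**Step 3, subject classes in the SOC row.**

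- Severity, taken from the reduced dataset: 2 mild + 1 moderate + 1 severe = 4, for 3 subjects. Subject 1 is both mild and moderate.
- Relationship, taken from the reduced dataset: 2 related + 1 possibly related + 1 not related = 4, for 3 subjects.
- With a maximum taken at SOC level: 1 mild + 1 moderate + 1 severe = 3, and 2 related + 1 not related = 3.

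**Step 4, if the Note governs the event column.** Epistaxis has 5 events, but their class is still undefined. By each event's own severity they are 4 mild and 1 moderate. At each subject's maximum they are 2 mild and 3 moderate, because subject 1's two mild bleeds are moved up. The SAP does not say which applies.

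**Step 5, bounds for the 14-day Phase I group (Protocol 2.4.2).** There were 46 related AEs in 6 subjects, or 46/6 = 7.7 per subject. The split by preferred term is not given.

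- Fewest kept: one term per subject, 6 of 46 = 13%.
- Most kept: no term repeated within a subject, 46 of 46 = 100%.

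The documents do not narrow this range.

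**The case against.** The strongest reply is that the two rules can be read together: the maximum classifies subjects, and the Note governs the event column. On that reading nothing collapses. This is a fair reading and probably the intended one, but the text does not state it. The severity and relationship sentences apply the reduced dataset to the whole summary, and the reconciled reading still leaves the class of each event open (step 4).

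Several stronger conclusions that a reader might draw are not supported:

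- **That repeat bleeds disappear from the report.** They remain in the unreduced SOC and preferred-term table and in the listing of all AEs. The general summary table, whose introduction promises event numbers, has a drug-related category.
- **That all event counts fall to subject counts.** This holds only in preferred-term rows.
- **That the SAP instructs multiple counting of subjects in SOC rows.** It gives no SOC rule. Multiple counting follows only if those rows are taken straight from the term-level dataset.
- **That harm on ALX-0081 is understated by a known factor.** The 14-day Phase I rates were 7.7 related events per subject on ALX-0081 and 1/2 = 0.5 on placebo, but the placebo rate is one event in two healthy volunteers. The 7-day group shows a much smaller contrast: 13/6 = 2.2 against 2/2 = 1.0. Without the split by term, no loss can be calculated for either group.

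It also stands that the rule keeps each subject's worst severity and most conservative relationship per term, so no severe or related finding is lost at subject level in preferred-term rows. Safety is analysed descriptively without formal tests (Protocol 10.3), and the safety stopping rule sits in a separate DSMB plan and charter (SAP 6.6 and 6.7). No formal trial conclusion depends on these columns.

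**Conclusion.** The point holds as an internal contradiction and a missing rule. Applied as written, the dataset rule gives wrong event columns in the two tables that report events by preferred term with severity or relationship, and those columns conflict with the Note and with the plain SOC and preferred-term table. If events do repeat within a term, the arm with more repeats loses more of them. How many cannot be said from the documents: the 14-day Phase I group gives only the range 6 to 46 of 46. In SOC rows a subject can appear in more than one class because no SOC-level maximum is defined. This should be corrected before the tables are programmed. It affects the reading of a descriptive secondary safety endpoint, not the primary analysis or the stopping rule.

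**What to change.** Amend SAP 6.4.1 as follows.

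1. State that the dataset reduced to one record per subject and term feeds only the columns for number and percentage of subjects.
2. Count events in both tables from all treatment-emergent records, each under its own severity or relationship. Counting at the subject's maximum is a possible alternative convention, but it relabels mild repeats as more severe.
3. Link records that exist only because an AE worsened (Protocol 9.1.3) and count the episode once at its maximum severity, as the Note requires. Use the same linked records in the plain SOC and preferred-term table so that the totals agree, and state which relationship a linked episode takes when its records differ.
4. For subject columns, derive worst severity and most conservative relationship separately at SOC level and at preferred-term level.

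The cost is a few sentences in the SAP and minor reprogramming. No new data are needed, provided that AE start and stop dates, which the SAP already relies on, are complete enough to link worsening records.
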